Data Entry: We will use several strategies to augment and evaluate the quality of data entry: 1) standardized forms, e.g., for laboratory test orders, subject interviews, and

medical record data abstraction; 2) structured data entry through a secure, serverbased database system, e.g., MS Access; 3) double entry of standardized forms with routine error checks, e.g., every third subject; and 4) automated checks for value changes across observation points, e.g., sudden increase or decrease in symptom levels – flag values for additional review.

Additional Quality Checks: We also will perform complementary quality checks: 1) routine checks for missing values; 2) cross-validation of data (e.g., psychiatric symptom levels) by comparing study data vs. medical record information for a random sample of subjects; 3) cross-validation of adherence data: (a) self-report vs. (b) RA pill counts vs. (c) medical record (plus EHR/LMR for the two Partners clinics) vs. (d) APCD pharmacy records (both study arms – includes capture of any drugs prescribed by non-psychiatrists and/or dispensed by pharmacies);[135-137] and 4) periodic trend checks to identify and confirm large changes in any outcome or covariate values. During follow-up, we will ask any subjects who forget to bring their drugs to a visit for the pill count to bring their drugs in to their next clinical appointment for a "catch up" pill count. We will use a standardized process for addressing imputation of missing values or reconciliation of different values.

VI. Biostatistical Analysis

Analysis of Aim 1: Treatment: By design, all subjects in the Intervention arm will start by being under treatment. During the course of follow-up (FU), we expect that some will stay consistently on treatment, some will discontinue treatment (become non-adherent), while others will make transitions on and off treatment in various patterns (e.g., subsequent modifications made by any PCP and/or changes in adherence over time). In contrast, by design, subjects in the Usual Treatment (control) arm do not start on treatment; however, some will initiate treatment as a result of usual clinical care, e.g., PCP initiation. For this aim, in which we study treatment use at various time points, only an intent-to-treat (ITT) approach is relevant since whether or not subjects are on treatment is the outcome itself.

Characterization of Usual Treatment: We also will carefully describe care under Usual Treatment, including the timing of initiation, treatment choice, adherence, prescribing clinicians, and visit patterns for subjects in the control arm. We will characterize the involvement of other clinicians for subjects in both arms, and clinic traits.

Treatment Operational Definition: To start, we will use the same treatment definition for both study arms, i.e., current use of a statin and angiotensin drug. Because there are multiple potential drugs for cardiovascular prevention, we will alter this definition in a series of sensitivity analyses. For example, we will examine a minimal cardiovascular treatment variable in which we define treatment as current use of any cardiovascular drug, independent of the therapeutic class or mechanism of action. We also will examine a partial treatment variable in which we count the number of distinct cardiovascular prevention drugs.

Analysis approach 1: We will plot the percent on "adequate" CVD prevention care, at baseline and the four quarterly follow up times to monitor how treatment activity unfolds over time in the two arms of the trial. At any given follow-up point we will be comparing

two binary outcomes (on or off treatment) and will use standard methods for comparing two proportions to test statistical significance and get confidence intervals for the difference in the percent on treatment in the two arms. We will use a Bonferroni correction so the four separate tests or CIs will have an overall level of 0.05 or 95% CI, respectively.

Analysis approach 2: We will use all available follow-up data to construct a summary measure of the mean percentage of follow-up time during which each group was on treatment. Since we expect the distribution of outcomes to be non-normally distributed, we will get a test of significance for no difference between the mean outcomes in the two arms using a randomization test. A 95% confidence interval for the difference of percentage of time on Tx will be obtained using bootstrap methods. We will use STATA 13.0 for all analyses.

Analysis of Aim 2: ITT Effect on Cardiovascular Risk Factors: For aim 2, our primary outcome is the difference in summary risk level changes (e.g., modified Framingham score) between our two study groups, i.e., do intervention subjects experience differential changes in cardiovascular risk levels compared to control subjects. This outcome will be continuously measured (but not necessarily normally distributed).[138-140] We will also examine individual risk factor levels, including LDL, SBP, and HbA1c. By virtue of randomization and given the size of our study, the mean baseline values will be very close to equal, with the profile of the mean levels of the outcomes diverging over time. Our main analytic strategy is to use an ITT analysis, such that subjects provide data for the group to which they were randomized regardless of protocol adherence. Initially, we will get descriptive plots showing the profile of mean outcome over time in each group. This plot will be suspect if missing data (e.g., loss to follow-up) do not occur completely at random (MCAR). For more definitive analysis, we will use methods for analysis of repeated measures data that provide valid estimates of the profiles of mean outcomes over time under the weaker, missing at random (MAR) assumption that allows the probability of missing data to depend on measured characteristics. We also expect that the outcomes will be non-normally distributed based on our past experience in studying adherence. This likely bimodal adherence distribution could induce a corresponding bimodal distribution in the changes in outcome levels. All of the outcomes are likely to show this sort of non-normality. The HbA1c data also could be skewed. In general, we will therefore use analysis methods that are robust to nonnormality.

For analysis of the repeated outcomes data, we will use econometric-style OLS linear model analysis of the repeated mean levels of the outcome over the five observation times (baseline + four follow-up times). This approach is robust to non-normal distributions. For constructing standard errors we will use cluster and heterogeneity robust estimation methods. Among estimation methods for this model, we will emphasize the use of the "fixed effects" (FE) option, which can be implemented in STATA using the xtreg command with the FE option. This essentially amounts to change score analysis that is generalized for use in situations with more than two repeated measures. This will provide estimates of the profiles of mean change from baseline in each of the treatment arms along with significance tests for contrasts between the two profiles. For plotting, the profiles of change will be anchored at the observed mean values in each arm at baseline. Inverse Probability (IP) weighting

methods will be used to account for possible endogenous loss to follow up in connection with the proposed analysis. Weighting will be based on baseline characteristics and for any given subject; the same weights will be applied to each repeated measure. We will finalize our analytic protocol before examining the outcome data, i.e., a priori delineation of the analytic protocol as is becoming the standard of analysis. We will use only marginal distributions to guide the appropriateness of the final choice of methods. Thus, we mitigate the potential for bias resulting from post-hoc choice of analysis or significance testing.

Analysis of Aim 3: Per-Protocol Effect on Cardiovascular Risk Factors: For Aim 3, we will study the same composite and individual risk factor outcomes as for Aim 2, but will estimate the per-protocol effect rather than the ITT effect. ITT is the effect of assignment to the strategies of interest; the per-protocol effect is the effect of following the strategies as indicated in the protocol and is the implicit target of inference. To estimate the per-protocol effect, however, one needs to make assumptions similar to those commonly made in the analysis of observational studies. Specifically, when adjusting for measured covariates, the valid estimation of the per-protocol effect requires that all fixed and time-varying factors that jointly predict the outcome and adherence to the assigned intervention are measured without error. We will adopt two analytic approaches, both involving adjustment via inverse probability (IP) weighting. Analysis approach 1: We will artificially censor participants when they stop adhering to the assigned strategy. We will censor subjects in the active treatment arm if/when their adherence drops below 80% of the intended dose, based on estimates of the proportion of days covered (PDC). [141-144] In sensitivity analyses, other adherence cutoff points will be used, as in our other past studies.^[145] For subjects in the control arm, we will follow two censoring strategies: (i) subjects will be censored if/when they start taking one of the drugs assigned to the active treatment arm, (ii) subjects will never be censored, which is equivalent to interpreting any treatment they receive as standard of care. We will conduct separate analyses under each of these two censoring strategies. We will compare the average outcome between arms at pre-specified time points during the follow-up. The outcome models will be similar to those described for Aim 2, but they will be fit to those remaining uncensored at the corresponding time. This approach requires no assumptions about the dose-response curve for adherence because only adherent subjects contribute to the fit of the outcome model.

Analysis approach 2: We will estimate the parameters of structural models that specify the dose-response curve for adherence in the treatment arm. We will use a flexible dose-response function that incorporates information on both cumulative dose and recency, and builds on previous trial data. This analytic approach is more statistically efficient because it does not involve artificial censoring, but will require extensive sensitivity analyses to ensure that the estimates are not sensitive to the choice of dose-response function.

Power Calculations: We anticipate having adequate power for this trial. To illustrate, we will focus on comparison of treatment use at one time point. By design, all subjects in the intervention arm will receive cardiovascular prevention treatment, while none in the control arm (usual treatment) will have started treatment. At each follow-up time point,

some intervention subjects could be non-adherent (no use), and some control subjects could have started treatment (use). We will test the significance of (with confidence intervals) the difference in the percent on treatment between the two study arms at each time point separately, using Bonferroni multiple comparison methods (exam-specific alpha=0.05/4 to get an overall test with alpha=0.05). Based on the literature, <15% of control subjects might initiate treatment. With one-sided alpha =0.0125 and 150 subjects in each comparison group (classifying subjects lost to follow-up as not on care so that sample size is constant), we estimate having 80% power to detect a 26% difference in use, and 90% power to detect a 20% in cardiovascular treatment use. We also have adequate power (90%) to detect clinically sensible cardiovascular risk changes (e.g., one standard deviation change in LDL levels in the absence of treatment), using modified two-sample normal theory and comparable assumptions (details available on request).

VII. Risks and Discomforts

The core of the intervention involves the administration of new medications, albeit medications that are already recommended by the guidelines, i.e. the trial will assess a population-based approach to provide patients with recommended guidelines, compared with usual practice. We have selected the population-based approach of using the same fixed moderate dose intervention for all eligible subjects randomized to the intervention arm. This ensures that any complications and adverse events are minimized. Nonetheless, any treatment intervention is associated with certain potential adverse events. In this study, we consider 2 categories of concerns: inadvertent disclosure of confidential information, and medication associated side effects.

Disclosure of confidential information:

One potential risk is a breach of the subjects' confidentiality. This could lead to their employer, insurance company, or others finding out that the subject participated in a research study. We minimize this risk by assigning each participant with a subject code to ensure that any protected health information is stored separately from clinical and diagnostic information. Study data to be analyzed will be stored on password-protected computers or else in locked filing cabinets in locked offices. Participants are informed of these potential risks in the consent form. Names of subjects will not be used in any publication of research results. Thus the identities of individual participants will be known only to the research team.

Medication associated side effects:

Common side effects for simvastatin include headache, abdominal pain, constipation, nausea, and upper respiratory infection. There is an increased risk of skeletal muscle effects (e.g. myopathy and rhabdomyolysis) with doses 80mg or higher.

Common side effects for losartan are diarrhea, muscle cramps, insomnia, nasal congestion, dizziness, low blood pressure, and syncope (fainting).

Common side effects for atorvastatin include diarrhea, insomnia, nausea, and upper respiratory infection (common cold). There is an increased risk of skeletal muscle effects (myopathy and rhabdomyolysis) with higher doses. Patients might experience pains or stiffness in the arms and legs if that happens. In addition, there is also an increased risk of stroke or transient ischemic attack at doses of 80mg.

Common side effects for valsartan are diarrhea, joint or back pain, insomnia, fatigue, dizziness, low blood pressure, and syncope (fainting).

Since we are using low to moderate doses of these generic medications and they have had few complications with large amounts of trial and post-marketing data, we expect any adverse effect to be rare and low intensity. Nonetheless, we will handle adverse events as follows:

Any adverse events due to any cause that occurs during the course of this trial, whether or not related to the study medication, will be reported to the Partners IRB, the NIMH, and the FDA in a written report including demographic information and a narrative explanation of the event. The study nurses will inform the study PIs, who will then determine whether to discontinue the medications; this determination could involve members of the DSMB. For example, if a subject reports mild self-resolving fatigue that does not appear to be temporally associated with the study medications, we would record the event for the appropriate reports but could determine that the event was unlikely to a) be related to the medication; b) pose a clinically meaningful risk to the subject. In contract, should a subject report difficulty breathing and the nurse reports signs of edema, we would immediately stop the medication and make sure the subject receives immediate, appropriate treatment.

Several alternative medication treatments exist for reducing cardiovascular risks. Participants will be made aware of these alternative treatment options as well as the potential side effects of the study medications in the informed consent document to allow them to make an informed decision about whether to enroll in this study.

Psychiatric Evaluation:

Some participants might feel uncomfortable answering questions during the psychiatric evaluation. They will not be forced to answer if they do not wish to answer any particular question.

Blood Draws:

Blood draw may lead to a small arm bruise and, in rare cases, clot or infection at the site the blood was drawn. Some people become light-headed during or immediately after a blood draw. These are rare occurrences and in our experience the vast majority of participants tolerate blood draws well. Participants will be monitored for 15 minutes following the blood draws to ensure they are doing well.

VIII. Potential Benefits

It is hoped that results from this study can be used to implement cardiovascular care within mental health clinics. Since cardiovascular disorders are a main source of morbidity and mortality for SMI patients, such an intervention may constitute a major improvement in the health of this population. A fixed-dose combination of pills could serve as a useful tool for minimizing non-adherence to treatment. [57-61] Use of moderate doses also yields clinical benefits with fewer side effects and complications. [62-64] The intervention also could serve as a prevention strategy in behavioral health homes, an emerging new approach to unified care for patients with SMI.

IX. Monitoring and QA

We will capture all psychiatric and medical diagnoses and prescription drugs. We will identify and intervene on any subject who demonstrates unstable psychiatric or medical disease. Potential intervention triggers include finger stick glucose (FSG) levels > 200, QTc>500ms on ECG, or signs of diabetes, renal, or liver failure based on laboratory results. Note that the intervention focuses on cardiovascular prevention, and does not attempt to treat diabetes (though cardiovascular complications are a paramount clinical concern for diabetics); we do not believe that a fixed-dose approach is clinically appropriate for diabetes treatment. Other triggers include symptoms consistent with unstable angina, suicidal/homicidal ideation, or other unstable clinical situation in the judgment of the study staff. In these cases the PI will be notified by pager, and will authorize contact with the patient's psychiatrist and PCP; and in extreme cases, the PI may refer the patient to the emergency department (ED) for immediate evaluation. For subjects without a PCP, but not requiring emergency attention, we will refer the subject to a medical clinic suggested by the mental health staff at the study site. For these events occurring during screening, we will exclude subjects from the trial; for events occurring during the trial, we will report the event to the DSMB.

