Note that when a participant stops a first-line medication and starts a second-line medication, this will likely be out of cycle for our 90-day medication dispensation schedule. To maintain maximum flexibility of scheduling in those cases and to avoid waste, we will have the ability to dispense 45 tablets of the second-line medication instead of 90 so the participant can return for their next scheduled visit and subsequently go on the 90-day schedule.

As always, if a patient chooses to stop the study medication or becomes non-adherent with it despite our offer of second-line medications, we will note this information. Patients will not be offered second line medications in the event of a medically significant adverse reaction such as elevated CK or rhabdomylosis. Participants will only be offered second line medications when complaining of subjective side effects with no medical complications (e.g. headache or abdominal pain with no relevant changes in blood samples). Participants who start second line medications will be asked to return in 2-4 weeks for a safety check similar to when participants started the first line treatments.

Table 1: Assessments

Step 1: Recruitment

Clinicians review their list of scheduled patients to identify potential subjects and ask these patients if they are interested in a research study. If patients agree, the research team approaches them to describe the study, obtain consent, sign DMH authorization form (if applicable), sign the APCD access release (optional), and schedule initial visit.

Step 2: Eligibility Screening

RAs conduct initial interview

Study nurses collect (screening) blood samples and vital signs, e.g., weight and height, and blood pressure

RAs collect urine pregnancy tests for all women of childbearing potential.

After the screening laboratory tests are available, study nurses will assess the eligibility for each potential subject and conduct the initial safety check. For example, if there are any subjects who appear to have signs of active cardiovascular disease or diabetes, we will intervene immediately via referral to PCP office or ED visit as appropriate.

Step 3: Baseline and Medication Visit (eligible subjects asked back for a medication visit)

Random assignment of eligible subjects into one of two study arms: Intervention vs. Usual Treatment

Subjects who are ineligible will have the option of participating as a Non-Randomized subject where study data will be collected.

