In order to receive a bonus, Follow-Up #2 and Follow-Up #3 need to be scheduled and attended within one month after the end of the scheduling window in order to receive the bonus. If the participant completes the visit outside of the scheduling window, they will still get paid the baseline payment of \$20.00. The scheduling window refers to the two-week window within which a visit is due, which is 83 days from the prior visit. A member of the study team will contact participants to let them know when visits are due.

- If a participant completes Follow-Up #1, then staff will compensate \$40.00 for Follow-Up #2.
- If a participant completes Follow-Up #1 and Follow-Up #2, then staff will compensate \$60.00 for Follow-Up #3.
- If a participant completes Follow-Up #1 or Follow-Up #2 (but not both visits), then compensation for Follow-Up #3 will be \$40.00

V. Study Procedures

Study Site: The study will take place at four sites: McLean Hospital, BayCove Gill Clinic, Mass Mental Health Center, Edinburg Center, and Massachusetts General Hospital Outpatient Bipolar Clinic. Study procedures will be the same at each site. Study staff will bring all study equipment, including study drugs, with them to the separate sites and carry out all study procedures, leaving no burden on staff from these sites.

Contacting patient's current treater: The only information to be shared with the PCP is the "PCP letter" (included in the IRB application). This letter will be sent out between the inclusion/exclusion visit, only for patients eligible to be randomized, and the randomization visit, when we find out what arm of the study the patient is going into. Since this letter is sent prior to randomization, the letter does not include information on what study arm the patient is assigned to. The letter states that the participant will be explicitly removed from the study if requested by the PCP for medical purposes. The logic of this design is as follows: ours is a randomized open-label study. The treatment as usual arm is intended to capture naturalistic primary care of our patients while the intervention arm tests the impact of a cardiovascular preventive regimen. In these trials, "contamination" across study arms is a major concern. This refers to a process

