Obtaining Study Drugs: Study nurse practitioners will prescribe study medication for subjects as follows: simvastatin 20 mg once per day, and/or losartan 25mg once per day or atorvastatin 10mg once per day and/or valsartan 40 mg once per day. The grant will pay for study medications at no cost to participants. The McLean Hospital Research pharmacy will procure the study medication for all study sites and dispense prescriptions in 3 month supplies. The study staff will pick up prescriptions from the pharmacy and provide to the subject during the study visit. Since the medications will be provided the same day, investigators will not store medications in any way, other than to transport the mediations to the various study sites. Study staff will follow the same procedures for procuring and dispensing medications at all external sites. That is, study staff will procure medications from The McLean Hospital Research pharmacy the morning of external site visits and transport the medications to dispense at each site.

Additional Data Sources: There are other noteworthy data sources for this trial: 1) clinic records; 2) electronic health records for two clinics; 3) APCD. RAs will systematically review the visit schedules and local medical records from each clinic for each subject. Additionally, McLean is scheduled to roll out its electronic health record (Epic Systems) during the course of this study, which we have extensive experience using in other settings. These data sources will provide complementary data sources for cross-validation (e.g., pharmacy fills, see quality checks below) as well as longitudinal information on psychiatric visit adherence, primary care visit frequency, and major unfavorable clinical events, e.g., ED visits and hospitalizations for psychiatric or cardiovascular events.

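### A 90-tablet supply can run out before the latest visit day the protocol accepts or rewards, leaving gaps of up to about 30 to 37 days in the intervention arm that the plan does not say how to count

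*Protocol*

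**What the plan says.** **Supply.** Protocol section V, Obtaining Study Drugs, has the research pharmacy "dispense prescriptions in 3 month supplies". First-line dosing is "simvastatin 20 mg once per day, and/or losartan 25mg once per day"; the second-line drugs are also once daily. On delivery: "The study staff will pick up prescriptions from the pharmacy and provide to the subject during the study visit". The Trial Study Design Overview says of a switch to a second-line drug that "this will likely be out of cycle for our 90-day medication dispensation schedule", and for that case "we will have the ability to dispense 45 tablets of the second-line medication instead of 90". Neither document describes an overage, a bridging supply or a between-visit refill for a late visit. The 45-tablet option covers only a switch to a second-line drug.

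**Visits.** Table 1, Step 4, sets follow-up visits every 3 months. Section IV, Compensation, adds: "The scheduling window refers to the two-week window within which a visit is due, which is 83 days from the prior visit". Follow-Up #2 and #3 must be scheduled and "attended within one month after the end of the scheduling window in order to receive the bonus". The next sentence there says that a visit completed outside the scheduling window earns only the base $20.

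**Outcomes.** The SAP words its primary outcome in two ways: first as the proportion of the 12 follow-up months with any of the prescribed medication, then as a number of days on both drugs (or on the one eligible drug). Protocol Aim 1 uses current use at each follow-up point. For Aim 3, analysis approach 1: "We will censor subjects in the active treatment arm if/when their adherence drops below 80% of the intended dose", estimated from the proportion of days covered (PDC).

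**The concern.** The supply is sized for about 90 days, while the visit rules tolerate, and for two visits appear to reward, a longer interval. A participant who takes every tablet can then have no drug until the next visit. Intervention participants depend on study visits for their study drug; control participants obtain drugs through ordinary care. A gap created by the trial's own logistics can therefore arise in the intervention arm only.

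Two results are exposed. Under the SAP's day-count wording, each day without supply lowers the intervention arm's value on the primary outcome. In Aim 3, a supply gap can push days covered below 80% and censor someone who missed nothing that was available. The trial asks whether its design supports high adherence, so a reader will need to tell supply gaps from participant behaviour.

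**Working it through.** The plan states no coverage figure, so there is none to reproduce.

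**Inputs.** One tablet of each drug per day and 3-month supplies (section V, Obtaining Study Drugs). A 90-day dispensing schedule (Trial Study Design Overview). A tablet count of 90 is written only for the second-line drugs; for the first-line drugs it is inferred from once-daily dosing and the 90-day schedule. Two-week window, day 83, one-month bonus limit (section IV, Compensation). 80% cut-off (section VI, Aim 3).

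**Assumptions.** No leftover stock; the prior visit is the previous dispensing visit; one month is 30 days, with 28 to 31 as the range.

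**Formulas.** Gap = interval − 90. Maximum interval coverage = 90 / interval.

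The text does not say whether the window opens on, is centred on, or closes on day 83, so all three are shown.

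| Window | Window end: gap, coverage | Bonus limit | Gap at limit | Coverage at limit |
|---|---|---|---|---|
| Opens day 83 (83–97) | 7 days, 90/97 = 92.8% | 97 + 30 = day 127 (125–128) | 37 days (35–38) | 90/127 = 70.9% (70.3–72.0%) |
| Centred on day 83 (76–90) | none | 90 + 30 = day 120 (118–121) | 30 days (28–31) | 90/120 = 75.0% (74.4–76.3%) |
| Closes day 83 (69–83) | none | 83 + 30 = day 113 (111–114) | 23 days (21–24) | 90/113 = 79.6% (78.9–81.1%) |

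**Where 80% becomes impossible.** 90 / 0.80 = 112.5, so from day 113 no participant can cover 80% of the interval.

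**Over a 365-day year, for someone who takes every available tablet:**
- Intervals of 83 or 90 days: 4 × 90 = 360; 360/365 = 98.6%.
- Every visit at day 97 (fills at 0, 97, 194, 291): 90 + 90 + 90 + 74 = 344; 344/365 = 94.2%.
- Follow-Up #1 at day 90, then two visits at the 127-day limit (fills at 0, 90, 217, 344): 90 + 90 + 90 + 21 = 291; 291/365 = 79.7%.
- The same path with a 28-day month (fills at 0, 90, 215, 340): 270 + 25 = 295; 295/365 = 80.8%.
- The same path with the window centred on day 83 (fills at 0, 90, 210, 330): 270 + 35 = 305; 305/365 = 83.6%. Cumulative coverage is lowest at day 330: 270/330 = 81.8%.

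**Dependence on the scoring rule.** At day 127 an empty bottle gives 90/90 = 100% as tablets taken over tablets dispensed, but 70.9% as days covered. Under the SAP's month wording, intervals of 90/127/127 days leave 11 of 12 months with some drug, and 97/127/127 leave 12 of 12.

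**The case against.** The nominal schedule fits the supply: visits every 3 months, drug for 3 months. Visits on days 83 to 90 leave no gap, and the worst visit inside the window still gives 92.8%. The larger gaps need attendance at the end of a payment period that applies to Follow-Up #2 and #3 only, and that sits badly beside the base-only payment for visits outside the window. If the bonus were confined to the window, the lowest bonus-eligible coverage would be 92.8%. All of this stands, and it limits the size of the problem.

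Four stronger readings are tempting, and the documents do not support them.

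- *Fully adherent participants will be scored as off treatment or below 80%.* Neither document says how days without supply are scored, which denominator PDC uses, or how far back current use looks. The month wording of the primary outcome absorbs most gaps.
- *Annual coverage falls below 80%.* The 79.7% figure misses the line by 0.3 points and needs two consecutive last-day visits on one reading of the window. A 28-day month gives 80.8%; the centred window gives 83.6%.
- *The gaps bias the intention-to-treat result.* The outcome is use under each strategy, and dispensing at study visits is part of the intervention. Days without drug are real non-use. Ordinary care may have refill gaps too.
- *Run-out days should be exempt from Aim 3 censoring.* That would keep people without drug in the analysis as adherent and dilute the contrast the analysis aims at.

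The 80% rule also reaches only the per-protocol work, which the SAP calls supplemental. The protocol plans other cut-offs and a second approach without artificial censoring.

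**Conclusion.** The supply and visit rules do not agree. On every reading of the window, a bonus-eligible visit can fall after the tablets have run out: by about 30 to 37 days on the two main readings, and about three weeks if the window closes on day 83. Even inside a window of days 83 to 97 the supply can be 7 days short.

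These are upper bounds. They assume one tablet per drug per day, no leftover stock, a 30-day month and the literal reading of the one-month bonus limit. Nothing in the documents says how often late visits will occur, so no expected effect on the trial result can be given.

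For the intention-to-treat primary outcome, the consequence is avoidable real non-use in the intervention arm, visible under the day-count wording and mostly hidden under the month wording. For Aim 3, the consequence is possible censoring caused by supply rather than behaviour, depending on a PDC denominator that is not defined. The point merits correction but does not undermine the primary analysis.

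**What to change.** **Protocol.** Reconcile the 90-day dispensing schedule (Trial Study Design Overview), the 3-month supplies (section V, Obtaining Study Drugs) and the visit and bonus rules (section IV, Compensation), so that the supply dispensed and the latest visit day the protocol accepts or rewards agree. The sponsor decides which side changes. In the same edit, state where the two-week window lies relative to day 83, and resolve the conflict between the one-month bonus limit and the base-only payment outside the window.

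**SAP.** Derive each participant's run-out date from the dispensing records. Keep days after run-out as non-use in the intention-to-treat primary outcome, and report their number separately. State the PDC denominator. Examine the effect of run-out days on Aim 3 censoring as a sensitivity analysis, without exempting them from the main rule.

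**Cost.** Depending on the sponsor's choice, some extra generic tablets, or a tighter bonus limit that may lose a few late visits. Beyond that, one derived variable and one sensitivity analysis; no extra participants or procedures.
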